4.2.9.2. Reporting of adverse events

The sponsor or designated person is responsible for reporting the AAG to the Research Ethics Committee and for providing it with all relevant initial and follow-up information about the event. The researcher must keep a copy of all AAG information in his or her file, including correspondence with the sponsor and the Research Ethics Committee.

The researcher must keep copies of all AAG information in a file, including correspondence with the sponsor.

The sponsor or designated person shall notify the relevant Authorities of all relevant and unexpected information on AAG suspected of being related to the study medication, causing death or threatening life, as soon as possible and in any case within a maximum period of seven days of becoming aware of them. Relevant follow-up information on these cases will be notified subsequently, within an additional eight days.

Any other serious and unexpected event suspected to be related to the study medication, as soon as possible, but within a maximum period of fifteen days after the investigator becomes aware of them. The researcher should keep a copy of all relevant security information in his or her file.

-Contact details of the promoter (coincides with the fact that he will be the person in charge of communicating the AA):

[name]

Son Llàtzer University Hospital, Internal Medicine Service

[contact]

[contact], [name]

4.2.10. Sample size calculation

In the first version of the study, the sample size has been calculated considering the context of the first COVID outbreak and taking into account that it was a unicentric study, so the following was considered:

Given that this is a unicentric study in which the experimental treatment is applied in certain phases and on specific days, and that depends on the ability to obtain donors and patients with specific characteristics, added to the context in which it is carried out, in which the number of patients hospitalized in HUSLL decreases every day, adding the factor that in the Balearic Islands the number of hospitalized has been lower, added to not having any definitive data so far that allows us to calculate the sample size safely and due to the urgency of the situation. It is required to collect the plasma sample from patients discharged from HUSLL and apply it to all those hospitalized patients who agree to participate in the study after being informed and signing the informed consent, both those hospitalized in the COVID-19 plant and in the HUSLL ICU. This is further justified if we consider the fact that currently in HUSLL there are less than 100 patients admitted for COVID-19, which is a low number, taking into account also that not everyone will want to participate. Therefore, plasma must be collected, and treatment applied to all those who sign the informed consent.

In this new version of the study (version 2.0) the context of the study changes, since it is a multicentre study, and the epidemiological framework is slightly better known. Therefore, the sample size is estimated as follows:

Since from the beginning of the pandemic to the present day no effective treatment against SARS-CoV-2 infection has been found; whereas it has also been shown that the disease has a high probability of progressing rapidly into more severe forms, causing death even in vulnerable groups; whereas the forecast for late summer-start autumn 2020 is being met; whereas there are no prevalence/incidence numbers or any other type of definitive numerical data that allows canonical sample size calculations to be made; whereas the few studies that have been published on the treatment of hyperimmune plasma infection have shown a positive trend towards decreasing symptoms and severity; and that finally we continue to find ourselves in a health emergency situation; so for all these reasons this study is transformed into a multicentre study, at the request of the participating centres. Therefore, it is required, in order to estimate with maximum efficiency, the effect of this therapy, the maximum number of donors and the maximum number of possible recipients. Each case is explained below:

-For donors: it is required to collect the plasma sample from the maximum number of people who meet the requirements to be donors. This aims to create an anti-SARS-CoV-2 hyperimmune plasma bank, so that not only for this study, but for serious situations in which all the possibilities available so far have been exhausted, this therapy can be used as an alternative. The difficulty of finding suitable donors, who not only meet the requirements to be donors, but also have a sufficient antibody titration, forces us to make accurate donor lists in order to have this type of sample in sufficient quantity. Being a multicentre study, more doses of plasma will be needed to be able to supply all the centres. Considering that the ratio is 1 donor or 1 donation for each recipient.

-For recipients: as it is unknown how many patients can progress in the coming weeks/months with COVID-19, it is required to propose participation in the study to all patients who are diagnosed with COVID-19 and admitted to the plant or ICU for COVID-19 of all participating centres. In this way, the maximum number of patients can be collected, in order to cover a sufficient sample size in the two branches of comparison of the study (control and treatment). As patients are admitted, they will be proposed to participate by explanation and with the HIP, and if they sign the IC, they will become part of it.

4.3. Development of the study: work plan and data collection

RECRUITMENT CIRCUIT:

[figure not shown]

Fig 2. Outline of the development of study.

4.3.1. Stages of study and evaluation of the response

a) The study procedures for the patient receiving treatment shall be carried out as follows:

1. Baseline visit/screening:

- Review of inclusion and exclusion criteria: HIP and CI signature.
- Vital signs: Blood pressure, Heart rate, Respiratory rate, Temperature, and oxygen saturation.
- Complete physical examination.

- Review of relevant medical history.
- Rx of Tx
- Electrocardiogram.
- Weight, height, Body mass index.
- ECOG.
- Complete hematology.
- Coagulation study, D-dimer.
- Arterial blood gas.
- Biochemical analysis: Glucose, creatinine, glomerular filtration (CKD-EPI), sodium, potassium, chlorine, or rhea, urate, calcium, ferritin, C-reactive protein, AST, ALT, GGT, FA, LDH, CPK, troponin, procalcitonin.
- Inflammatory parameters: IL-6.
- Serology HIV, HVC, HVB, SYPHILIS.
- Imaging tests according to usual practice.
- Real Time-PCR for detection of Coronavirus SARS-COV-2 in nasal smear and pharynx.
- Quantitative determination of antibodies (IgG, IgM) against Coronavirus SARS-COV-2.
- Immunohematological study (ABO Group, Rh, Indirect Coombs).
- Concomitant medication evaluation.

2. Treatment initiation visit (First dose: day 1): Marked procedures (*) do not need to be repeated if performed at baseline in the previous 7 days:

- Study treatment assignment: if it is an intervention group, first plasma infusion.
- Vital signs (TA, FC, FR, T^a) pre-infusion and post-infusion*.
- Complete physical examination*.
- ECOG*.
- Hematology*.
- Biochemical analysis*.
- Inflammatory parameters*.
- Concomitant medication evaluation.
- Evaluation of emerging adverse effects.

3. Visit of Day 2:

- if it is an intervention group, second plasma infusion.
- Concomitant medication evaluation.
- Evaluation of emerging adverse effects.

4. Visit of Day 3:

- Vital signs (TA, FC, FR, T^a).

- Physical examination.
- ECOG.
- Hematimetry.
- Biochemical analysis.
- Inflammatory parameters.
- Nasal and pharyngeal smear for RT-PCR of Coronavirus SARS-COV-2.
- Quantitative determination of antibodies (IgG, IgM) against Coronavirus SARS-COV-2.
- Concomitant medication evaluation.
- Evaluation of emerging adverse effects.
- Clinical/virological response evaluation.

5. Visit of Day 7:

- Vital signs (TA, FC, FR, T^a).
- Physical examination.
- ECOG.
- Hematimetry.
- Biochemical analysis.
- Inflammatory parameters.
- ECG.
- Nasal and pharyngeal smear for RT-PCR of Coronavirus SARS-COV-2
- Quantitative determination of antibodies (IgG, IgM) against Coronavirus SARS-COV-2.
- Concomitant medication evaluation
- Evaluation of emerging adverse effects.
- Clinical/virological response evaluation.

6. Visit of Day 14:

- Vital signs (TA, FC, FR, T^a).
- Physical examination.
- Hematimetry.
- Biochemical analysis.
- Nasal and pharyngeal smear for RT-PCR of Coronavirus SARS-COV-2.
- Quantitative determination of antibodies (IgG, IgM) against Coronavirus SARS-COV-2.
- Concomitant medication evaluation.
- Evaluation of emerging adverse effects.
- Clinical/virological response evaluation.

7. Visit of Day 21/end of study (at discharge):

- Vital signs (TA, FC, FR, T^a).
- Physical examination.

- Rx of Tx to assess evolution/resolution of infiltrates.
- ECG.
- ECOG.
- Hematimetry.
- Biochemical analysis.
- Inflammatory parameters.
- Real Time-PCR for SARS-COV-2 viral load study.
- Quantitative determination of antibodies (IgG, IgM) against Coronavirus SARS-COV-2.
- Concomitant medication evaluation.
- Evaluation of emerging adverse effects.
- Clinical/virological response evaluation.

IMPORTANT: In cases where the patient is discharged after 7 days, visits on day 14 and day 21 can be made on an outpatient basis, in outpatient consultations or day hospital, after appointment with the patient.

Screening visits and day 1 may overlap on the same date threaten life the inclusion criteria are confirmed and none of the exclusion is met.

There will be a margin of +/- 24 hours to perform the procedures of visits 7, 14 and 21 (to be able to adjust the appointments in external consultation).

The study procedures for study subjects (control and treatment groups) can be reviewed in summary form in the following table:

Procedure	Study days						
	Screening/ Basal	Day 1*	Day 2	Day 3	Day 7	Day 14	Day 21
DATE							
Signature of informed consent	X						
Medical history review	X						
Physical examination	X	X*		X	X	X	X
Vitals signs	X	X*		X	X	X	X
Weight, Height, BMI	X						
ECOG	X	X*		X	X	X	X
ECG	X				X		X
ABO/Rh Group	X						
Hematimetry	X	X*		X	X	X	X
Coagulation	X	X*		X	X	X	X
Biochemistry	X	X*		X	X	X	X
Study of inflammatory parameters	X			X	X		X
Serology Important IgG/IgM anti-COVID	X			x	x	x	x
Quantitative titration antibodies	X			X	X	X	X
COVID PCR	X			X	X	X	X
Chest Rx	x						x
AE Review	X	X	X	X	X	X	X
Concomitant review	X	X	X	X	X	X	X
Clinical response	X			X	X	X	X
PLASMA TRANSFUSION		X	X				

Table 3. Summary of procedures in the study subjects.

LEGEND:

- DATE:** indicate the patient's follow-up date.
- Screening/Basal VISIT:** this visit corresponds to the moment the patient signs the informed consent.
- DAY 1:** corresponds to the time of the first plasma transfusion.

EXPLANATION:

- SCREENING/BASAL VISIT AND DAY 1 MAY COINCIDE.** In this case it is not necessary to repeat the determinations of day 1. The marked procedures (*) do not need to be repeated if they were performed at the screening visit in the previous 7 days.

b) The study procedures for the plasma donor subject are as follows:

1. Basal visit:

- Review of inclusion and exclusion criteria: HIP and CI signature.
- Extraction of nasal/pharyngeal smears for the determination by RT-PCR of Coronavirus SARS CoV-2.
- Serum extraction for determination of antibodies (IgG, IgM) SARS-COV-2.
- Serological determinations.
- Complete physical examination.

2. Visit for the performance of plasmapheresis: Performance of the procedures as set out in point 4.2.6

4.3.2. Duration of the study

In version 1.0 of the study, the estimated study duration period was 3 months from the date of compliance with the Clinical Research Ethics Committee (in Spain CEIm) Research Ethics Committee (CEIm) and Spanish Agency for Medicines and Health Products (in Spain AEMPS). In this version 2.0 the study period is extended to recruit a sufficient n to be able to estimate the effectiveness of the treatment or failing that until the competent authorities so determine. The follow-up period for patients will be 21 days from the start date of the study and if necessary, it will be extended as long as necessary, in order to ensure patient safety.

4.3.3. Primary and secondary variables

The variables that will be collected will be those related to the study of the efficacy, tolerance, safety and clinical effects of the treatment. Below is the list of encoded variables:

VARIABLE NAME	UNITS	CODING	VALUE
Diagnostic date			Date
Date of birth			Date
Age	years		Number
Presence of concomitant disease		0	Yes
		1	No
Concomitant disease species			Name

Sex		0	Man
		1	Woman
Weight	Kg		Number
Height	cm		Number
Body mass index	Kg/cm ²		Number
Physical examination		0	Normal
		1	Clinically insignificant abnormality
		2	Clinically significant abnormality
Physical scans specify			Number
Blood pressure	mmHG		Number
Heart rate	lpm		Number
Respiratory rate	rpm		Number
Temperature	°C		Number
Oxygen saturation	%O ₂		Number
ECOG		0	Asymptomatic. Fully active.
		1	Intense activity restriction. Capable of daily work.
		2	Ambulatory and capable of self-care. Unable to work. Lifted more than 50% of the time awake.
		3	Capable of some self-care. Bed-chair life more than 50% of the time awake.
		4	Total disability. Chair-bed 100% of the time awake.
		5	Dead.
Electrocardiogram		0	Normal
		1	Abnormal. Clinically not significant.
		2	Abnormal. Clinically significant.
Concomitant medication		0	No
		1	Yes
Chest X-ray			Assessment
Concomitant medication specifies			Name
ANALYTICAL PARAMETERS			
Haemoglobin	g/dl		Number
Haematocrit	%		Number

Leukocytes	x10 ⁹ /l		Number
Absolute lymphocytes	x10 ⁹ /l		Number
Absolute neutrophil count	x10 ⁹ /l		Number
Monocytes	x10 ⁹ /l		Number
Eosinophils	x10 ⁹ /l		Number
Basophils	x10 ⁹ /l		Number
Medium Corpuscular Volume	fL		Number
Platelets	x10 ⁹ /l		Number
Prothrombin time	s		Number
Activated Partial Thromboplastin Time (APTT)	s		Number
INR			Number
Fibrinogen	mg/dl		Number
D-dimer	mg/dl		Number
Glucose	mg/dl		Number
Creatinine	mg/dl		Number
Glomerular filtration (CKD-EPI)	ml/min		Number
Sodium	mEq/l		Number
Potassium	mEq/l		Number
Chlorine	mEq/l		Number
Calcium	mg/dl		Number
Urea	mg/dl		Number
Urate	mg/dl		Number
Albumin	mg/dl		Number
Total proteins	mg/dl		Number
Iron	µg/dl		Number
Ferritin	ng/ml		Number
Ferry	mg/dl		Number
transferrin saturation index	%		Number
Reactive protein C	mg/dl		Number
AST	U/L		Number
ALT	U/L		Number
GGT	U/L		Number

LDH	U/L		Number
FA	U/L		Number
CPK	U/L		Number
Troponin I			Number
Procalcitonin			Number
IL-1			Number
Blood pH arterial blood gas			Number
PO ₂	mmHg		Number
HIV Serology		0	Negative
		1	Positive
HVB Serology		0	Acute infection
		1	Chronic infection
		2	Past infection
		3	Immunized
		4	Negative
CMV Serology		0	Negative
		1	Positive
Syphilis Serology		0	Negative
		1	Positive
INMHEMATOLOGIC STUDY			
ABO Blood Group		0	A
		1	B
		2	AB
		3	O
Rh		0	Present
		1	Absent
Irregular Blood Group antibodies		0	Negative
		1	Positive
DIAGNOSTIC/MICROBIOLOGICAL PROCEDURES			
Quantitative titration of SARS-COV2 antibodies (IgG/IgM)		UA/mL	Number
RT-PCR SARS-COV-2		0	Negative
		1	Positive

Time to RT-PCR negativization	Days		Number
CLINICAL CRITERIA			
Pleural effusion		0	Negative
		1	Positive
PSI score		1	Valuation not required
		2	<=70
		3	71 - 90
		4	91 - 130
		5	>130
WHO Progression Scale		0	Uninfected; no viral RNA detection.
		1	Asymptomatic; viral RNA detection
		2	Symptomatic. Independent
		3	Symptomatic. Need for assistance
		4	Hospitalized. Oxygen-free
		5	Hospitalized. Oxygen with mask or nasal tips
		6	Hospitalized. Oxygen by non-invasive ventilation (NIV) or high flow.
		7	Intubation or mechanical ventilation. PO2/FIO2>= 150; or SpO2/FO2> 200
		8	Mechanical ventilation (pO2/FIO2< 150, or SpO2/FIO2< 200), or vasopressor (norepinephrine >0.3 microg/Kg/min)
		9	Mechanical ventilation (pO2/FIO2< 150, or SpO2/FIO2< 200), or vasopressor (norepinephrine >0.3 microg/Kg/min) o dialysis o ECMO
% of patients requiring ICU admission			Number
15-day mortality rate			Number
Mortality rate at 30 days			Number
Days of hospitalization			Number
SECURITY CRITERIA			
Emerging adverse effects (ASD) \geq GIII		0	No
		1	Yes
Type TEAE SPECIFY			Name
Cumulative rate/incidence of ASD \geq GIII in experimental branch			Number

Cumulative rate/incidence of emerging adverse events (ASD) any grade in experimental branch			Number
Hospital discharge date			Date
Exitus		0	Yes
		1	No

Table 1. Variables that will be included in the database of the study.

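### The WHO progression scale in Table 1 has no level for death, and its level 9 contains all of level 8, so any comparison of the scale as coded would be conditional on survival

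*Combined protocol and SAP*

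**What the plan says.** All wording below is from the combined protocol and SAP.

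- **Range of the scale.** Section 4.3.3, Table 1, lists the "WHO Progression Scale" under clinical criteria. It starts at 0, "Uninfected; no viral RNA detection", and ends at 9. The row after level 9 is a different variable, the percentage "of patients requiring ICU admission".
- **Top levels.** Level 7 is "Intubation or mechanical ventilation. PO2/FIO2>= 150; or SpO2/FO2> 200". Level 8 is "Mechanical ventilation (pO2/FIO2< 150, or SpO2/FIO2< 200), or vasopressor (norepinephrine >0.3 microg/Kg/min", with the bracket then closed. Level 9 repeats that text in full and continues to "or vasopressor (norepinephrine >0.3 microg/Kg/min) o dialysis o ECMO". The untranslated o is read here as or.
- **Death elsewhere in Table 1.** "15-day mortality rate" and mortality at 30 days are separate rows, and Exitus is a yes/no flag. ECOG level 4 is "Total disability. Chair-bed 100% of the time awake", and the next ECOG level, 5, is death.
- **Date of death.** Table 1 has a discharge date but no date of death. A field for it appears on the Annex V event form. Section 4.2.3 also sends the date of leaving the study to the medical history.
- **Handling of deaths.** Section 4.2.3 lists death among the reasons for removing a patient from the study. Section 5 has no rule for scoring a death on this scale, none for missing values, and no method named for the scale.
- **Timing.** The visit list in Section 4.3.1 calls for a clinical/virological response evaluation at days 3, 7, 14 and 21. It does not name the WHO scale at any visit.

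**The concern.** An ordinal severity scale is useful because it ranks every patient, including those who die. Here a patient who has died has no permissible value. If the codebook is followed, that patient is missing at every later assessment, and missing because of the worst possible outcome. If plasma changes mortality in either direction, the arms lose different kinds of patient and the remaining comparison is no longer the randomised one. A harmful treatment can look better on the scale, and a real benefit can be diluted.

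The overlap of levels 8 and 9 is a smaller matter of measurement. In an open, multicentre trial, two centres could score the same ventilated patient differently. The trial enrols ICU patients with SOFA above 6 (Section 4.2.1), so both the top levels and deaths are to be expected.

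**Working it through.** The documents give no expected mortality, sample size or power for this scale, so there is no plan figure to reproduce. The overlap can be checked by logic. The effect of dropping deaths needs assumed inputs, which are marked as such.

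**1. Overlap of levels 8 and 9.** Take four features: V = ventilation with pO2/FiO2 <150 or SpO2/FiO2 <200; P = the stated vasopressor dose; D = dialysis; E = ECMO. There are 2^4 = 16 combinations, of which 15 have at least one feature.

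| Reading of level 9 | Fits 8 and 9 | 8 only | 9 only | Neither |
|---|---|---|---|---|
| V or P or D or E (literal) | 12 | 0 | 3 | 0 |
| (V or P) and (D or E) | 9 | 3 | 0 | 3 |

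On the literal reading, level 8 lies wholly inside level 9. A rule that the highest level applies would leave level 8 unused. On the second reading, taking the highest level resolves the nine double fits, but dialysis or ECMO alone fits neither level. The patients whose score depends on the reading are those with V or P and no D or E, plus those with D or E alone. A minor gap of the same kind: SpO2/FiO2 of exactly 200 meets neither the level 7 nor the level 8 saturation criterion.

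**2. Deaths dropped, survivors alike in both arms (assumed mortality).** Let mt and mc be mortality on plasma and control. With death as the worst level and ties counted half, the probability that a plasma patient fares better is

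0.5(1−mt)(1−mc) + (1−mt)mc + 0.5·mt·mc = 0.5 + (mc − mt)/2.

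Among survivors it is 0.50 throughout. At the 1:2 control:treated ratio in Section 4.1, the share of patients with no codable final score is (mc + 2mt)/3.

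| mt | mc | Death as worst level | Uncodable |
|---|---|---|---|
| 5% | 10% | 0.525 | 6.7% |
| 10% | 20% | 0.55 | 13.3% |
| 15% | 30% | 0.575 | 20.0% |
| 20% | 10% | 0.45 | 16.7% |

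**3. A case where the direction reverses (assumed).** Suppose plasma moves 10% of patients from level 8 to death.

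| Level | 2 | 4 | 5 | 6 | 8 | Dead |
|---|---|---|---|---|---|---|
| Control % | 30 | 20 | 15 | 10 | 15 | 10 |
| Plasma % | 30 | 20 | 15 | 10 | 5 | 20 |

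- Survivors only, weighting each plasma level by the control patients who are worse plus half of those tied: (30×75 + 20×50 + 15×32.5 + 10×20 + 5×7.5)/(80×90) = 3975/7200 = 0.552, favouring plasma.
- Death as worst level: 0.30×0.85 + 0.20×0.60 + 0.15×0.425 + 0.10×0.30 + 0.05×0.175 + 0.20×0.05 = 0.4875, slightly favouring control.
- Survivor means: plasma 3.15/0.8 = 3.94, control 3.95/0.9 = 4.39. With death scored 10: plasma 3.15 + 2.00 = 5.15, control 3.95 + 1.00 = 4.95.

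**4. Power under a true benefit (assumed).** Severity is a normal latent variable cut into levels, with the top 20% of controls dead and plasma shifted by 0.45 SD. Plasma mortality is then 1 − Φ(0.84 + 0.45) = about 10%. The test is a two-sided Mann-Whitney at 0.05, simulated for four assumed sets of cut-points and 120 patients.

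| Allocation (control/plasma) | Death as top level | Deaths dropped |
|---|---|---|
| 60/60 | 54-65% | 27-42% |
| 40/80 (the 1:2 ratio) | 51-60% | 26-37% |

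**The case against.** The strongest reply is that deaths are not lost. The 15- and 30-day mortality rows, Exitus and ECOG 5 all record them, and Section 5 promises a description of every variable, so excess deaths on plasma would show there. This stands, and it limits the harm. It does not make a survivor-only comparison of the scale valid.

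A reader might infer that a primary endpoint is compromised. The documents do not support that. They name no primary variable, the main objective in Section 3.2.1 speaks of immunological efficacy, and the scale has no hypothesis, timepoint or test of its own.

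A reader might also infer that the sponsor plans a survivor-only analysis, with gaps at particular visits. The documents give no rule either way and do not tie the scale to a visit. What can be said is that the coding leaves no value for a death.

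Nor are levels 8 and 9 identical. Level 9 adds dialysis and ECMO, and on the literal reading those patients score 9 without doubt.

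The illustrations rest on assumptions. The reversal in step 3 is built in by the choice of inputs, and on ranks its harm side is small (0.4875 against 0.50). The 120 patients in step 4 come from no section. An extraction loss of a tenth level cannot be fully excluded, but the rows run unbroken into the next variable.

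**Conclusion.** The point holds as a coding and analysis gap that should be fixed. It falls short of a critical flaw because the scale is one unranked variable and mortality is recorded separately.

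Two things follow from the text alone: the scale has no value for death, and every level 8 criterion is also a level 9 criterion. The consequence is conditional: if the scale is compared as coded, the comparison is restricted to survivors.

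Its size depends on assumed mortality. The probability that a plasma patient fares better moves from 0.55 to 0.49 when mortality is 20% v 10%, and power falls from 51-65% to 26-42% in the benefit scenarios, depending on cut-points and allocation. If plasma has no effect on mortality or on who survives, dropping deaths costs information but should not bias the comparison.

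**What to change.** 1. Add 10 = Dead to the scale in Table 1 and carry it to every assessment after the death.
2. Add a date of death to Table 1, so that the carrying forward can be done from the study database.
3. Reword levels 8 and 9 so that each combination of supports falls in exactly one level, and assign SpO2/FiO2 of exactly 200. Which supports belong where is for the sponsor to settle against the scale's source.
4. State in Section 5 that the full 0-10 scale, deaths included, is compared between assigned arms with a rank-based or proportional-odds method, and name the assessment days. State that removal from the study at death (Section 4.2.3) does not remove the patient from this analysis.

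The cost is a codebook and case report form edit, one new date field, and a short addition to Section 5. Dates for deaths that have already occurred would have to be taken from event forms or medical records. Treatment and visits do not change. The edit should be made before any comparison by arm, because a scoring rule for deaths added after results are known would be open to challenge.

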darunavir/cobicistat; remdesivir), interferon- α/β , anti-IL-6 monoclonal antibody (Tocilizumab) or oxygen therapy among others. The ratio controls: treated will be 1:2 in favour of the treatment. As treatments have been changing throughout the pandemic, when performing the final analysis, a stratified analysis will be made by type of treatment. That is, infected patients who have been treated with the same drugs will be compared.

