5. DATA ANALYSIS: STATISTICS

A descriptive analysis of all variables will be performed. With the categorical variables, the global percentages and frequencies will be estimated. Normality tests and graphs will be used to determine if the quantitative variables follow a normal distribution. Normal distribution variables shall be expressed as mean \pm standard deviation and those without normal distribution shall be expressed as median and interquartile range. To describe the significance and associations between variables after the intervention, parametric and non-parametric tests will be used as appropriate (the student's t test of paired samples or the Wilcoxon test for quantitative variables and the ANOVA test for paired samples or Friedman test for qualitative variables). The correlations will be examined by the correlation of Spearman or Pearson ranges and a multivariate analysis will be performed to assess the effect of other factors such as the confusion/interaction effect, as well as to assess the possible construction of predictive models. A p-value $< 0,05$ shall be considered an indicator of a significant difference. SPSS v.23 software will be used for data analysis.

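### Length of stay and time to PCR negativity are recorded as plain numbers with no rule for death, continued stay or persistent positivity, so a default comparison could mislead

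*Combined protocol and SAP*

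**What the plan says.** Table 1 in section 4.3.3 includes "Days of hospitalization" and "Time to RT-PCR negativization". Each holds a number, without a stated time origin, end event, censoring indicator or code for death. The table does not separate primary from secondary variables.

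Section 5 summarises normal quantitative variables by mean and standard deviation, and "those without normal distribution shall be expressed as median and interquartile range". The tests it names for them are "the student's t test of paired samples or the Wilcoxon test for quantitative variables". It adds that "a multivariate analysis will be performed to assess the effect of other factors" without naming a model, and that p below 0.05 "shall be considered an indicator of a significant difference". It mentions no Kaplan-Meier, log-rank, Cox, cumulative-incidence or worst-rank method.

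Other relevant provisions:
- Section 4.3.2: "The follow-up period for patients will be 21 days from the start date of the study", extendable if patient safety requires it.
- Section 4.3.1: after screening, PCR is scheduled on days 3, 7, 14 and 21, with a 24-hour margin either way on the last three.
- Section 4.2.3: death is a reason for removal from the study, and the date of leaving goes into the medical history.
- Table 1: death is a yes/no item. Discharge date and mortality at 15 and 30 days are listed, but nothing links them to the two durations.

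**The concern.** Both variables are times to a favourable event that death can prevent. The trial enrols ICU patients with SOFA above 6 and lists mortality as an outcome, so deaths must be expected.

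For length of stay, a plain day count stops at death just as it stops at discharge. If deaths come early, they shorten the mean stay of the arm in which they occur, and the comparison can point the wrong way.

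For PCR clearance, a patient who dies before converting or is still positive at day 21 has no conversion time. A comparison of recorded times then covers converters only, a subset defined after treatment starts. Virological response is a stated secondary objective (section 3.2.2), so this comparison is likely to be reported.

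**Working it through.** The protocol states no sample size, effect size or expected mortality for the trial population, so there is no planned figure to reproduce. The inputs below are assumptions that show direction and rough size only.

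**Length of stay, by arithmetic.** Let m be mortality, D the day of death and S the survivors' stay. Then mean stay = m × D + (1 − m) × S. For two arms with the same D and S, the difference is (difference in m) × (D − S). Take S = 14 and mortality 10% v 20%.
- Early deaths, D = 7: 0.1 × 7 + 0.9 × 14 = 13.3; 0.2 × 7 + 0.8 × 14 = 12.6. The higher-mortality arm looks 0.7 days better.
- Late deaths, D = 20: 0.1 × 20 + 0.9 × 14 = 14.6; 0.2 × 20 + 0.8 × 14 = 15.2. The higher-mortality arm looks 0.6 days worse.
- Discharged alive by day 21: 90% v 80% in both cases. This ordering does not depend on when deaths occur.

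**Length of stay, by simulation.** The protocol says "The ratio controls: treated will be 1:2 in favour of the treatment", although section 4.1 also describes equal-probability assignment. The simulation used 50 control and 100 treated patients, gamma-distributed stays averaging 14 days in survivors and 6 days in those who die, and no true difference in survivors' stay. It ran 4,000 times with a two-sided Mann-Whitney test at 0.05. That is an unpaired test, which the protocol does not name.
- Mortality 10% in both arms: 4.9% of runs significant on raw days, 5.2% with deaths ranked worst. Both hold their size.
- 10% control, 20% treated: mean difference −0.8 days, and 11.8% of runs significantly favour the higher-mortality treated arm. With deaths ranked worst, this falls to 0.1%, and 17.0% − 0.1% = 16.9% are significant in the correct direction.
- 10% control, 30% treated: −1.6 days and 31.5% falsely favourable; 0% with deaths ranked worst.
- 20% control, 10% treated: treatment looks 0.8 days worse. Runs favouring treatment are 0.4% on raw days and 17.2% with deaths ranked worst.

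**PCR conversion.** Assume exponential conversion with median M, read at days 3, 7, 14 and 21. Without deaths, the share with no conversion time by day 21 is 2^(−21/M).
- M = 7: 2^(−3) = 12.5%.
- M = 21: 2^(−1) = 50%.
- With 20% mortality and deaths averaging day 8, the simulated shares are 22.1% and 56.7%.

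The mean recorded time among converters, without deaths, is 9.8 days for M = 7 and 12.2 days for M = 21. The true median triples, a gap of 14 days, while the converters' mean moves by 12.2 − 9.8 = 2.4 days.

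**The case against.** The strongest reply is that Table 1 is a database coding list, not an analysis rule. A reader might infer that the protocol counts a death as a short stay, or drops non-converters. It says neither, and it states no analysis set or missing-data rule. Both are only what happens by default if the recorded numbers are analysed as they stand.

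The named t test is also for paired samples. Each patient has one stay and one conversion time, so a paired test cannot compare the arms on them. The broader gap is that section 5 names no clear between-arm test for these variables. That is correct, but it does not answer the point: choosing between parametric and non-parametric tests, plus an unnamed multivariate model, supplies no rule for death or censoring.

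A reader might also infer that the stay comparison must flatter the arm with more deaths. The documents do not support this. They give no timing of death, late deaths are plausible in ICU patients, and the D = 20 case reverses the sign.

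Finally, this is a phase I pilot, neither variable is designated primary, and mortality and visit-level PCR results are listed separately. A mortality difference would therefore be visible beside the stay result. This limits the harm but does not correct either duration comparison.

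**Conclusion.** The concern holds as a gap with consequences. Neither Table 1 nor section 5 has a rule or method for death, continued stay or positivity at day 21. Following them by default could bias the stay comparison and would restrict the conversion comparison to converters.

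Under the assumed inputs, the stay distortion is 0.6 to 0.8 days per 10-point mortality difference, and its direction depends on whether deaths precede or follow survivors' discharge. Between 12.5% and 50% of patients would lack a conversion time without deaths, if the median is 7 to 21 days. None of these inputs comes from the protocol.

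It would go too far to say that the protocol prescribes the faulty handling, that the bias has a fixed direction, or that a primary result is affected.

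**What to change.** In section 5:
- **Hospital stay.** Compare the arms on time to discharge alive, with death as a competing event (cumulative incidence), or with deaths ranked worst. Define the time origin, and censor at the last follow-up within the 21-day period.
- **PCR clearance.** Compare the proportion alive and RT-PCR negative at days 7, 14 and 21, or time to first negative swab with death as a competing event and censoring at the last swab. Define what counts as negative.
- Name a between-arm test for each.

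In Table 1, add date of death. A reader might assume that it is already in the database, but Table 1 has only the yes/no item. A death date appears on the Annex V form, while section 4.2.9.1 centres adverse event recording on treatment-related events, and section 4.2.3 puts the date of leaving the study in the medical history.

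The cost is a little more analysis, new wording and one field. No visits or swabs are added.

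Days alive and out of hospital to day 30 is an alternative only if day-30 hospital status and readmissions are also collected. Planned follow-up is 21 days, and Table 1 has no readmission variable.
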